2.1 Objectives & Hypotheses	
Hypothesis: The development of alternative methods of screening for HCV infection in persons who inject drugs (PWID), as part of a harm reduction strategy at “Cañada Real” shantytown (Madrid), may facilitate diagnosis of the disease in this population, increase the frequency of referral to hospital and administration of appropriate HCV treatment and thus reduce the prevalence of HCV.
 
Objectives: The overall objective of this project is to evaluate whether the implementation of an alternative method of HCV screening in PWID from "Cañada Real " (Madrid) can improve the localization of HCV-infected patients for subsequent referral to the Hospital, administration of HCV antiviral therapy and cure of hepatitis C. The effectiveness of the intervention in each of the phases of the project will be assessed.
 
Main objectives:
 
 1. To develop and validate an alternative method of screening for active hepatitis C virus (HCV) infection based on collection of capillary blood via finger pricking and Whatman™ cards (dried blood). 2. Implementation of a screening program in PWID from "Cañada Real" (Madrid) aimed at early HCV detection (diagnostic) and early HCV treatment as part of a harm reduction strategy, and 3. To assess the effectiveness of our alternative HCV screening test in PWID through evaluation of the impact on the patients' health (referrals to health centers, number of treated patients, and the percentage of cure). 
Secondary objectives:
 
 4. Estimation of the prevalence of HVC active infection or HCV resolved spontaneously with the methodology developed. 5. To estimate the prevalence of other chronic viral infections (eg, HIV, HBV, and HDV) that are relatively common in PWID. 6. To estimate the prevalence of active HCV infection 24 months after the first intervention in “Cañada Real”. 7. To assess factors associated with HCV infection and transmission through an epidemiological survey, which will collect demographic data and risk behaviors.

**2.2
Background &
Rationale,
Significance of
Selected
Topic &
Preliminary
Data**

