
protocol.

The Whatman 903 cards used to collect whole blood will be handled by healthcare professionals. The device consists of a small card with five circles for collecting one drop of blood each. The card is attached to a record card where demographic information on the individual being tested is recorded. A small amount of capillary blood from the user's ring or middle finger is collected on the sample collection area and then allowed to dry at room temperature for three hours. The card is then made ready for transportation to the screening laboratory. It must be taken to the laboratory within 15 days of collection.

Samples will be sent to the CNM-ISCIH for laboratory testing. The cards will be stored at -80°C .

PHASE I: INTERNAL VALIDATION AND REFINING OF THE TECHNIQUE

Once the ethics committee has approved the study, samples will be obtained by finger pricking using Whatman 903TM cards at visits to the Internal Medicine department of HUIL. All patients visiting the department, for whom recent analytical data (serology results for HCV, HIV, HBV, and HDV, as well as HCV-RNA viral load and HCV genotyping collected during the previous 15 days) will be asked to take part in the internal validation study. Patients whose analyses were performed elsewhere or are not recent will not be included. Healthy individuals, i.e. those who have tested negative for HCV, HIV, HBV, and HDV will also be included. Individuals will be included in the validation consecutively until the preset number is reached (see below).

A total of 100 patients and 50 healthy individuals will be included to validate the screening test. Successive samples will be taken, and patients with genotypes 1a, 1b, 2, 3, and 4 will be included. National data indicate that the distribution of the most frequent genotypes in Spain is as follows: 1b, 44%; 1a, 26%; and 3, 20%. Therefore, these will be the genotypes most widely represented in our study. The 50 healthy individuals (negative for HIV, HBV, HCV, and HDV) will be obtained from the family members accompanying patients on medical visits, who will be invited to take part in the study. One dried blood sample will be taken by finger pricking and another simultaneous sample will be taken by venipuncture. The venipuncture sample will be processed through the usual channels at the center.

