Hepatitis C therapy will be prescribed according to European and regional guidelines. Current guidelines recommend treating PWID independently of the liver fibrosis stage. In this project, antiviral therapy will be chosen regarding interactions with other drugs or methadone and a once-daily therapy is preferred in those patients who decline being referred to a detox centre.

After HCV therapy has been completed, all PWID will be periodically screened for hepatitis C (analyzing RNA HCV) to detect infection. Depending on the drug users risk factors, screening for reinfection of HCV will be carried out on a 3 to 6 months schedule.

Infanta Leonor Hospital (HUIL) is the reference specialized health centre for Cañada Real shantytown. All PWID diagnosed of HIV and HCV in this shantytown are referred to the HUIL internal medicine department for evaluation. The hospital is highly coordinated with the harm reduction unit. Nurses or doctors from the harm reduction unit accompany the patients to the specialized clinic.

ETHICAL ISSUES

All patients will sign an informed consent form. Confidentiality will be maintained with regard to personal and genetic data in accordance with the basic ethical principles for research involving biological samples and the provisions of applicable legislation (Organic Law 15/1999 of 13 December on Data Protection, Law 41/2002 on Patient and Healthcare Autonomy and Law 14/1986 on General Health). The ethical research principles set out in the Declaration of Helsinki and the Belmont Report will be adhered to, as will those of the UNESCO Universal Declaration on the Human Genome and Human Rights. The requirements of Spanish legislation on processing on personal data will also be met. The research project has been approved by the Research Committee at HUIL and the Ethics Committee of Hospital General Universitario Gregorio Marañón and ISCIII.

LIMITATIONS OF THE STUDY

The study may be limited by the possibility of not reaching the required number of subjects, although we believe this to be unlikely given the large number of people who visit Cañada Real Galiana. Furthermore, the limit of HCV detection by real-time PCR is approximately 1000 IU/mL, although we believe that with this limit we may detect the vast majority of active infections, since HCV viral load in untreated patients tends to be greater than 1000 IU/mL. Moreover, previous publications show 94% sensitivity and specificity for the Whatman card.

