2.6 Study Duration

2.7 Statistical Analysis and Sample Size Justification

PHASE I

Once all subjects have been included, the results from the Whatman 903 cards will be compared with those obtained by venipuncture at HUIL. Diagnostic performance will be assessed by calculating the area under the ROC curve (AUROC) for each virus. The Se, Sp, PPV, and NPV for each virus will also be calculated.

PHASE II

Sample size: Assuming that around 10,000 people visit Cañada Real Galiana on different days, a sample size of 930 randomly selected subjects will suffice to estimate, with a 95% confidence interval and a precision of ± 3 percentage points, a

population percentage considered to be around 60%. A replacement rate of 0% has been anticipated.

PHASE III

In order to evaluate the effectiveness of the intervention, the accuracy of HCV tests will be calculated at the population level (AUROC, Se, Sp, PPV, and NPV), as will the percentage of patients arriving at the clinic, the percentage of patients treated, and the percentage of patients cured of hepatitis C. The incidence of HCV reinfection will be assessed using a Kaplan-Meier survival method. In addition, the effectiveness of the intervention for HIV, HBV, and HDV infection will be evaluated.

Statistical Methods

The statistical analysis will be performed using IBM SPSS Statistics for Windows, Version 22.0 (IBM Corp, Armonk, New York, USA) and the R statistical package, version 3.2.2 (GNU General Public License). All tests will be two-tailed, with p-values of <0.05 considered statistically significant.

An assessment will be performed to determine the percentage of patients who are positive at screening, are referred to a health center, have their diagnoses confirmed, and are treated at the end of the study. Factors associated with virus transmission, lack of referral to a health center, and HCV treatment will also be analyzed.

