Continuous variables will be presented as mean and standard deviation; categorical data will be presented as absolute numbers and percentages. The prevalence (95% confidence interval) of antibody for HCV, HIV, and HDV, HBsAg, and active HCV infection will be calculated in the sample and in the subgroups studied. Categorical data and proportions will be analyzed using the chi-square test or Fisher exact test, as required. The *t* test, ANOVA, or Mann-Whitney test will be used to compare continuous variables. The association study will be performed using logistic regression and adjusting for the major epidemiological and clinical covariates.

VARIABLES INCLUDED

PHASE I: VARIABLES TO BE RECORDED DURING INTERNAL VALIDATION TESTING

- Date of birth
- Gender
- Date of sample collection
- Date of last analysis
- HCV antibody result from last analysis (positive/negative)
- HCV-RNA result from last analysis
- Genotype result from last analysis
- HIV antibody result from last analysis (positive/negative)
- CD4+ lymphocyte count for HIV-positive patients
- RNA-HIV result for HIV-positive patients
- HDV antibody result from last analysis (positive/negative)
- HBsAg result from last analysis (positive/negative)
- DNA-HBV result from last analysis
- Incidents or errors in sample collection (yes/no)

PHASE II: VARIABLES TO BE RECORDED DURING SCREENING

- Code allocated
- Date of sample
- Date of birth
- Gender (male/female)
- Nationality
- Homeless (yes/no)
- No. of days per week that the individual visits Cañada Real Galiana
- Drugs consumed (mark as relevant):
 - Heroin
 - Cocaine
 - Marihuana
 - Alcohol
 - Benzodiazepines
- Current use of parenteral methods (yes/no)
- Date when parenteral methods were first used
- Frequency of injections (daily [No. of times]/weekly [No. of times])
- Syringe sharing for >3 months (yes/no)
- Frequency of syringe sharing (daily/weekly/monthly)
- Date of switch from parenteral methods to smoking
- On methadone program (yes/no)
- Being monitored for HCV infection (yes/no)
- Have you previously been offered the chance to undergo HIV and/or HCV testing?
 - No
 - Yes, but I did not accept
 - Yes, with (positive/negative) results for HIV and (positive/negative) results for HCV
- Contact with health center (never, occasionally, regular monitoring).
 - Primary health care
 - Hospital
 - Drug abuse center
 - Other
- Advantages of alternative screening
- Drawbacks of alternative screening
- Contact data provided (yes/no)

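### Phase I tests anti-HCV specificity on healthy relatives, the only HCV-negative group it describes; the result may not transfer to drug users, and Phase III cannot correct it

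*Combined protocol and SAP*

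**What the plan says.** Section 2.3 (Phase I, internal validation) sets the sample: "A total of 100 patients and 50 healthy individuals will be included to validate the screening test". Patients are invited if they have recent "serology results for HCV, HIV, HBV, and HDV, as well as HCV-RNA viral load and HCV genotyping collected during the previous 15 days", and the text adds that "patients with genotypes 1a, 1b, 2, 3, and 4 will be included". The controls are described separately: "The 50 healthy individuals (negative for HIV, HBV, HCV, and HDV) will be obtained from the family members accompanying patients on medical visits". Each person gives a finger-prick card and a venous sample at the same time.

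Under ELISA in the same section, card samples that are antibody-negative are tested no further, and positives go to real-time PCR. No second antibody assay on the card is named.

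Section 2.7 plans an AUROC for each virus in Phase I and adds: "The Se, Sp, PPV, and NPV for each virus will also be calculated". For Phase III it plans the same accuracy measures in the screened population. Section 2.3 says that those contacted and offered referral in Phase III are the people who screened positive. The variable lists in section 2.7 include the hospital laboratory's HCV antibody result.

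Secondary objective 4 in section 2.1 is "Estimation of the prevalence of HVC active infection or HCV resolved spontaneously with the methodology developed". The only accuracy figure in the document is under Limitations of the study in section 2.3: "previous publications show 94% sensitivity and specificity for the Whatman card".

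**The concern.** A specificity estimate is only as relevant as the negatives it comes from. Infected patients compared with healthy relatives who are free of all four viruses is an easy contrast. The test will be used where HCV-negative people may carry HIV or HBV, inject drugs, or have other illness, and antibody assays may give more false positives there. For HIV, HBV and HDV, HCV patients without the virus in question can serve as clinically realistic negatives. For HCV no such group is described.

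What is at stake is limited but specific. A false-positive ELISA goes to PCR and comes back RNA-negative. It therefore cannot inflate active infection, but it is indistinguishable on the card from past, cleared infection. Antibody prevalence, the resolved class of objective 4, and the claim that the ELISA is validated for this population all depend on a specificity measured elsewhere.

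**Working it through.** **Plan's own figure.** Section 2.7 gives 930 for a proportion of 60%, precision ±3 points, 95% confidence, population 10,000.
- n0 = 1.96² × 0.6 × 0.4 / 0.03² = 1024.4
- n = 1024.4 / (1 + 1023.4/10,000) = 929.3, rounded up to 930. It reproduces. No comparable justification is given for the 100 + 50 of Phase I.

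**Inputs for the size of the effect.**
- Screened: 930 (section 2.7).
- Antibody prevalence P: 60%, with 40% as an alternative. Section 2.7 does not say whether its 60% is antibody or active infection; reading it as antibody is an assumption.
- RNA-negative share of antibody-positives: 1 − 1.2/1.7 = 29.4%, from the general-population figures in section 2.2. Applying it to drug users is an assumption.
- Sensitivity (Se) and specificity (Sp): 94% each (section 2.3, Limitations), varied below.

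**Antibody prevalence.** Net bias = (1 − P)(1 − Sp) − P(1 − Se).
- P = 60%: false positives 372 × 0.06 = 22.3; false negatives 558 × 0.06 = 33.5; net −11.2 people, or −1.2 points.
- P = 40%: false positives 558 × 0.06 = 33.5; false negatives 372 × 0.06 = 22.3; net +11.2 people, or +1.2 points.
- At P = 60% the net is positive only if (1 − Sp) exceeds 0.6/0.4 = 1.5 times (1 − Se).

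**Resolved class (antibody-positive, RNA-negative).** Net change = false positives − true RNA-negatives missed by the ELISA.

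| P | True RNA-negatives | Sp | False positives | Net, Se 94% | Net, Se 100% |
|---|---|---|---|---|---|
| 60% | 558 × 0.294 = 164.1 | 94% | 22.3 | 22.3 − 9.8 = +12.5 | +22.3 |
| 60% | 164.1 | 98% | 7.4 | −2.4 | +7.4 |
| 60% | 164.1 | 99% | 3.7 | −6.1 | +3.7 |
| 40% | 372 × 0.294 = 109.4 | 94% | 33.5 | 33.5 − 6.6 = +26.9 | +33.5 |
| 40% | 109.4 | 98% | 11.2 | +4.6 | +11.2 |
| 40% | 109.4 | 99% | 5.6 | −1.0 | +5.6 |

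As a share of 930, the two 94%/94% rows are +1.3 and +2.9 points.

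**Precision of the Phase I estimate.** With 50 of 50 correct, the exact (Clopper-Pearson) lower 95% limit is 0.025^(1/50) = 92.9%. A test with true specificity 96% shows no error in 0.96^50 = 13% of such validations. This depends on the number 50, not on who the 50 are.

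**Can Phase III supply the specificity?** Specificity needs the true negatives. Card-negative people are not verified against venous blood, so Phase III observes true and false positives among those who attend. That is a positive predictive value in attenders.

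**The case against.** The strongest reply is that Phase I is only calibration and that population-level accuracy is assigned to Phase III, where the hospital antibody result is already recorded. What stands is that Phase III can expose false positives among people who attend. It still cannot give a specificity, because the negatives are not verified, and the plan itself expects many to refuse referral.

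Second, the plan does not say that all 100 patients are antibody-positive; the Phase I antibody variable allows either value. That stands, and the point is therefore limited to what is described. A required HCV genotype makes antibody-negative patients unlikely.

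Third, nothing in the document shows that specificity is lower in drug users than in relatives, and the 94% is quoted for the card, not for the ELISA. Both are correct. The transfer problem is a plausible spectrum effect, not a demonstrated one.

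A reader might infer that field false positives are certainly understated, or that antibody prevalence will be inflated. The document supports neither. At 94%/94% and 60% prevalence, antibody prevalence is biased downwards. Counting false positives alone (+2.4 points) ignores the larger number of false negatives.

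Finally, the resolved class has other sources of error: viraemia below the PCR limit of about 1000 IU/mL, and anyone already cured by treatment.

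**Conclusion.** The point holds as a weakness of the validation design, not as a demonstrated bias. The described HCV-negative group is unlike the people to be screened, and no later phase yields a valid specificity for them. Active infection defined by RNA is largely protected.

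The exposed result is the resolved class: a net gain of about 12 people at 60% antibody prevalence and about 27 at 40%, if sensitivity and specificity are both 94% and 29.4% of antibody-positives are RNA-negative. At 98-99% specificity the effect is small and, with 94% sensitivity, can be slightly negative. The sign of the bias in antibody prevalence is not fixed. The change is worth making because it is cheap and bears directly on main objective 1, not because a large error has been shown.

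**What to change.** In section 2.3, Phase I, keep the total at 150 and the paired card and venous samples. Fill as many of the 50 HCV-negative places as feasible with anti-HCV-negative patients seen in the HUIL Internal Medicine department, seeking HIV-positive patients, HBsAg-positive patients and drug users. Waive the genotype requirement for them. Complete the number with relatives if needed.

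In section 2.7, Phase I, report anti-HCV specificity with an exact 95% interval separately for these patients and for any relatives kept.

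In section 2.7, Phase III, describe the comparison of card and hospital antibody results among card antibody-positive, RNA-negative attenders as a positive-predictive-value check, and do not present it as population-level specificity.

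Cost: protocol wording and slower Phase I enrolment, with the same number of subjects and samples. Specificity may look slightly worse. Precision stays limited: 92.9% as the lower limit for 50 of 50, and wider in each subgroup (for example 0.025^(1/25) = 86.3% for 25 of 25). Recruiting all 50 from the field would cost more: at 60% positivity about 50/0.4 = 125 people of unknown status would have to be tested, with added venepuncture. That is why the hospital department is the practical source.

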Participants will be given an information leaflet and a specific informed consent form. Samples will be processed according to the study protocol (Annex 1). Clinical and epidemiological data will be recorded in a database that can be accessed by researchers from the HUIL and the CNM-ISCIH. The variables shown in section 2.4 will be recorded. This file has been included in the Register of Data Files of the ISCIH.

ELISA: A disc with a sample of dried blood will be placed in a microtube containing 300 μl of 0.5% buffer solution (PBS/BSA) and processed at $4-8^{\circ}\text{C}$ for 18-24 hours. After incubation, elutes from the dried blood samples will be tested for the presence of antibodies against HCV, HIV, and HDV, as well as for HBV surface antigen (HBsAg). Negative samples will not undergo further testing and will be considered non-infected. Positive samples will be tested using real-time PCR to confirm the positive results.

Real-time PCR: Nucleic acids will be extracted using the DSP virus pathogen kit (QIAGEN, Hilden, Germany). The samples will be stored at -80°C until use. A specific HCV test will be performed to confirm active HCV infection (HCV-RNA positive) on a Rotor Gene Q unit (QIAGEN).

PHASE II: SCREENING AT CAÑADA REAL GALIANA

Screening for HCV and the other viruses (HIV, HBV, and HDV) covered by this project will take place at Cañada Real Galiana. Screening will be conducted by nursing personnel hired specifically for that purpose. An active search will be made for

individuals who come into the shantytown from outside, and the detection test will be offered to everyone regardless of whether or not their serological condition is already known. Selection of individuals for screening will be random and consecutive.

Nursing personnel will generally be accompanied by an educator from the HRU. PWID will be offered information on prevention and the importance of early diagnosis and referral to health centers.

Information will then be provided on the goals of the study, and persons who agree to take part will be required to sign an informed consent form, provide contact data for subsequent location, and provide basic social and demographic data and information on their consumption habits. Regardless of whether or not individuals agree to take part in the study, they will all be given a card containing basic information on prevention and contact data for the internal medicine department of HUIL and the HRU.

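### Phase I plans no antibody-positive/RNA-negative group and runs PCR only on ELISA-positive cards, so the specificity of the RNA step cannot be usefully estimated

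*Combined protocol and SAP*

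**What the plan says.** Section 2.1 sets main objective 1 as "To develop and validate an alternative method of screening for active hepatitis C virus (HCV) infection". Secondary objective 4 then asks for the prevalence of active infection and of spontaneously resolved infection, using the method so developed.

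Section 2.3, Phase I, fixes the validation sample: "A total of 100 patients and 50 healthy individuals will be included to validate the screening test". Patients are those with recent results on file, covering serology for the four viruses "as well as HCV-RNA viral load and HCV genotyping collected during the previous 15 days". The case mix is given by genotype: "patients with genotypes 1a, 1b, 2, 3, and 4 will be included". For the controls: "The 50 healthy individuals (negative for HIV, HBV, HCV, and HDV) will be obtained from the family members accompanying patients on medical visits".

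The ELISA and real-time PCR paragraphs of the same section set the laboratory order. Eluates go to ELISA first. For reactive cards, "Positive samples will be tested using real-time PCR to confirm the positive results". For the others, "Negative samples will not undergo further testing and will be considered non-infected".

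Section 2.7, Phase I, plans AUROC, sensitivity, specificity and predictive values for each virus. It does not separate the antibody step from the RNA step.

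**The concern.** A positive HCV antibody shows past or present exposure. Only the RNA result tells an active infection from a resolved one. In Phase II the people on whom PCR specificity matters are those who are antibody-positive and RNA-negative: a false-positive PCR, for instance from contamination, labels a resolved infection as active.

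Phase I gives that step almost nothing to be tested on. The patients are selected in a way that makes viraemia likely, and the controls should stop at the ELISA. A specificity will still be reported for HCV, but it will mostly be the specificity of an antibody ELISA in healthy relatives. A reader could take it as evidence that the card separates active from resolved infection. At stake are the split in secondary objective 4 and the number of people referred who turn out not to be viraemic.

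**Working it through.** **The plan's own figure.** The 100 + 50 in Phase I comes with no target accuracy, precision or formula, so there is nothing to reproduce.

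**Step 1: which RNA-negative cards reach PCR?**
- Controls (50): they reach PCR only through a falsely reactive ELISA.
- Patients (100): no number of RNA-negative patients is set, and the genotype requirement makes them unlikely. The guaranteed number is 0.

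The expected number of controls reaching PCR is 50 × (1 − ELISA specificity), and the chance of none is specificity^50. The documents give no ELISA specificity. The limitations text in section 2.3 quotes 94% sensitivity and specificity for the card without naming the assay, so all three values below are assumptions.

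| Assumed ELISA specificity | Expected controls reaching PCR | Chance of none |
|---|---|---|
| 94% | 50 × 0.06 = 3 | 4.5% |
| 98% | 50 × 0.02 = 1 | 36% |
| 99% | 50 × 0.01 = 0.5 | 61% |

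**Step 2: what can so few cards show?** If all n are correct, the exact (Clopper-Pearson) 95% lower limit is 0.025^(1/n).
- n = 1: 2.5%
- n = 2: 15.8%
- n = 3: 29.2%

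If some of the 100 patients happened to be antibody-positive and RNA-negative (an assumption), 10/10 would give 69.2% and 20/20 would give 83.2%. The plan secures neither.

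**Step 3: what can Phase I estimate?**
- RNA sensitivity, given a reactive ELISA. If all 100 patients are viraemic, 94/100 gives 87.4% to 97.8%.
- Specificity of the full algorithm in the 50 controls. A result of 50/50 gives a lower limit of 0.025^(1/50) = 92.9%.

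**Step 4: does algorithm specificity reveal the PCR step?** In antibody-negative people, algorithm specificity = 1 − (1 − ELISA specificity) × (1 − PCR specificity). With ELISA at an assumed 94%:
- PCR specificity 50%: 1 − 0.06 × 0.50 = 97.0%
- PCR specificity 94%: 1 − 0.06 × 0.06 = 99.6%

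The gap is 2.6 points, or 1.3 of 50 controls. A poor PCR step and a good one would look alike.

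**Step 5: the remedy.**
- PCR on every control card: 50/50 gives a lower limit of 92.9%, now for the PCR itself, though in antibody-negative people.
- Thirty antibody-positive/RNA-negative patients: 30/30 gives 0.025^(1/30) = 88.4%.
- Sensitivity with 100 − 30 = 70 viraemic patients: 66/70 (94.3%) gives 86.0% to 98.4%, against 87.4% to 97.8% for 94/100.
- Genotypes other than 1b, 1a and 3: section 2.3 gives national shares of 44%, 26% and 20%, which leaves 10%. That is about 10 of 100 patients, or 7 of 70.

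**The case against.** The method being validated can fairly be read as the whole algorithm, and that has 50 controls for specificity and up to 100 patients for sensitivity. This stands. A reader might infer that Phase I cannot validate the active-infection test at all, and the documents do not support that. The gap is confined to the specificity of the RNA step.

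A reader might also infer that every patient is viraemic and that RNA-negative patients are excluded. Viraemia is not a stated criterion. The Phase I variables in section 2.7 record HCV antibody as positive or negative and list "HCV-RNA result from last analysis" without restriction. The genotype requirement makes RNA-negative patients unlikely, but it does not rule them out.

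Phase III records the card RNA and the hospital RNA, and section 2.7 plans accuracy at population level. A false-positive card would therefore be visible among those referred, and confirmatory bloods at the first hospital visit limit the harm to individuals. It is too strong to say that false positives could never be seen. The check comes after roll-out, however, and depends on accepting referral, which section 2.3 expects many to refuse. Section 2.3 also does not say whether a positive result means ELISA or RNA, so people who are ELISA-positive and PCR-negative may never have the reference test.

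Sample handling is delegated to Annex 1, and the flowchart figures are not shown. The Phase 1 task list mentions extraction of nucleic acid and antibodies from the cards without limiting it to ELISA-positive ones. This lowers confidence somewhat, but the rule in the main text is explicit.

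The data list's references to the last analysis might suggest a reference result up to 15 days old. Sections 2.3 and 2.7 name the venous sample as comparator, so this is at most ambiguous labelling and forms no part of the point.

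**Conclusion.** The point holds for the specificity of the RNA step. As written, Phase I guarantees no RNA-negative card a PCR. It would supply about 0.5 to 3 by chance if ELISA specificity lies between 99% and 94%, and 3/3 correct supports only a lower limit of 29.2%. Algorithm specificity in healthy relatives does not fill the gap.

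This rests on the ELISA-first rule applying in Phase I as the text states, on the assumed ELISA specificities, and on few or no RNA-negative patients among the 100.

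The documents give no reason to think that the PCR step is poor. The finding is that the planned data could not show whether it is. Because main objective 1 and secondary objective 4 both turn on active infection, a cheap change before Phase I starts is worthwhile. Analysis cannot recover the information if the PCRs are not run and the patients not enrolled.

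**What to change.** 1. In Phase I only, run dried-blood PCR on all 150 cards whatever the ELISA result. This also shows any viraemic patients whom the ELISA misses. Phase II can keep the ELISA-first order.
2. Within the same 100 patients, admit a set number of anti-HCV-positive/RNA-negative patients and waive the genotype requirement for them. Thirty is an example, not a derived figure. Report their specificity apart from that of the 50 controls: pooling gives 80/80 a lower limit of 95.5%, but it mixes two kinds of negatives, and the group that matters reaches 88.4%.
3. In section 2.7, report antibody accuracy and RNA accuracy separately, each with exact 95% limits.

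**Cost.** About 50 more PCRs on cards already collected, and no extra participants. Enrolment is no longer purely consecutive. With 30 places reserved, about 7 instead of 10 patients would have a genotype other than 1a, 1b or 3, and the RNA sensitivity interval widens slightly (66/70: 86.0% to 98.4%, against 94/100: 87.4% to 97.8%).
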